### Ablation procedure in the Tailored group

In the Tailored group, the procedure endpoint is sinus rhythm conversion by ablation at dispersion regions mapped during AF and potential subsequent AT(s).

Once mapping is complete:

- 1) The operator starts by ablating all dispersion areas. Tailored-PV-encircling along dispersion regions is recommended during dispersion areas ablation (cf. Figure 2). Ablation should always be done in a manner to either cover the dispersed electrograms or encircle a large area of dispersed electrograms (cf. Figures 3 and 4)
- 2) The operator then completes the isolation of the 4 PVs
- 3) The electrical connection of the 4 PVs is checked at the end of the procedure according to each site routine practice. Additional perivenous ablation can be performed to electrically disconnect the connected PV(s).

 Tailored-PVI or Tailored-PV-encircling corresponds to PVI or PV-encircling along dispersion areas around the PVs in order to optimize the flow of the procedure.

[figure not shown]

Figure 2: Tailored-PVI after Tailored-PV-encircling

In case of failure to terminate AF after ablation of all dispersion areas, at least one re-mapping/re-ablation is mandated, and two complete re-mappings are recommended. If the patient did not convert to sinus rhythm with ablation, a DC electrical cardioversion is performed.

If sinus rhythm is restored before ablation at all dispersion areas, the completion of the ablation set is mandatory, except in the atrial regions positioned close to the esophagus, phrenic nerve, AV node and/or sinus node. This list is not exhaustive, the operator can identify and document any other potentially hazardous areas for ablation.

When a sustained AT results from the ablation of all dispersion areas, mapping and ablation of AT must be performed with the use of activation maps  $\pm$  VX1  $\pm$  pacing maneuvers.

In case of linear ablation performed for macro-reentry (roof, perimital, cavo-tricuspid isthmus (CTI) flutter), lines should be validated by establishing a post-ablation bidirectional block. The impossibility of performing the line validation must be documented. No line validation is required without documented macro-reentry.

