#### Ablation procedure in the Anatomical group

In the Anatomical group, the procedure endpoint is isolation of all four PVs, documented according to each site routine practice (e.g. bidirectional block with mapping catheter).

The operator creates a contiguous circular lesion around each pulmonary vein antrum (1-2 cm from the ostia) with point-by-point applications of RF energy. If the patient is not converted to sinus rhythm at the end of the procedure, a DC electrical cardioversion must be performed.

No RF applications outside the PV antra are allowed (cf. Figure 6 (b)). RF applications at the carinas are allowed (cf. Figure 6 (a)).

[figure not shown]

Figure 6: RF applications (a) allowed at the carinas and (b) forbidden outside PV antra

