### Data collection

Table 7: Main data collected during procedure (complete list in eCRF)

Data	Description
Procedure times	Procedure start: Time of insertion of first sheath for vascular access Procedure end: Time of removal of sheaths
Voltage maps	Baseline Voltage maps performed blindly by the operator. In the Tailored arm, the baseline Voltage map is performed during VX1-guided mapping. In the Anatomical arm, the baseline Voltage map is performed during fast-anatomical mapping.
RA/LA volumes	RA/LA volumes in mL without veins
Mapping times	Time of start and end of each AF mapping for Tailored group Time of start and end of fast-anatomical mapping for Anatomical group
Ablation times	Time of start and end of each ablation cycle
Mapping picture	Only for Tailored group Picture of the biatrial shell with electroanatomic dots and VX1 dots before ablation start
Fluoroscopy time and dose	Total fluoroscopy time and dose for the entire procedure
RF times	Total RF ablation time and RF time to AF termination
RF Power	Min, Max and most commonly used RF power value
Ablation surface area	Total ablation surface area and ablation surface area to terminate AF, when the 3D navigation system allows it
Post-ablation picture	Picture of the biatrial shell with ablation tags for both arms and crucial dots for tags for both arms
Crucial dots	Crucial dots* number and location (cf. Figure 7)  *Crucial dots = AF/AT termination points or 20-ms cycle length increase

Ablation of VX1-tagged regions	Location and justification of VX1-tagged regions not ablated by the operator
AT data	Number, mechanism, and location (cf. Figure 7) of ATs
Procedure endpoints documentation	Pictures confirming PV electrical isolation, AF termination, SR conversion, lines validation (if applicable)
Medication administration	All cardiac medications administered during the procedure
Devices and equipment	Devices and equipment used during the procedure including diagnostic and ablation catheters, 3D navigation and EP recording systems

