### 7.3 – Risks associated with participation in the clinical investigation

Subjects randomized into the Tailored arm of the study are expected to receive higher RF times, greater ablation area, and slightly longer procedure times than subjects randomized to the anatomical arm. However, previous research indicates that RF time, ablation area, and procedure time while using the VX1 system are well within accepted industry standards for AF ablation and consistent with other approaches to AF ablation in published literature. The study design assumes that all patients receive the standard of care and expect additional benefits linked to close and repeated follow-ups after AF ablation.

The procedures and methods for data collection required by the protocol do not differ from routine AF ablation and post-ablation follow-up practice, other than filling out a Quality-of-Life questionnaire at baseline and at each follow-up visit.

	CLIPL-01-002-E	CONFIDENTIAL
	CLINICAL INVESTIGATION PLAN	F 09 XX 01 Rev.A Page 36/47

Use of the device not in conformance with this investigational plan and/or with the instructions in the physician's manual could introduce other issues.

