4.4 EXPLORATORY ENDPOINTS

The following endpoints compared in anatomical vs. tailored groups will be considered exploratory:

- 1. Freedom from documented AF, after one or two procedures, with or without AADs, at 12 months
- 2. Freedom from documented AF or AF/AT, after one procedure, or one procedure or more, without AADs, at 12 months
- 3. Freedom from documented AF or AF/AT, after one procedure, or one procedure or more, without AADs or with previously failed AAD at the same dose, at 12 months
- 4. Freedom from documented AF or AF/AT, after one procedure, or one procedure or more, with or without AADs, at 12 months, without the use of TTM
- 5. Freedom from documented symptomatic AF or AF/AT, after one procedure, or one procedure or more, with or without AADs, at 12 months
- 6. Freedom from AF or AF/AT, with or without AADs, 12 months after one procedure, or one procedure or more, for subjects with persistent AF <1 year.
- 7. Freedom from AF or AF/AT, with or without AADs, 12 months after one procedure, or one procedure or more, for subjects with AF ≥ 6 months (including long-standing persistent AF)
- 8. Estimated AF or AF/AT burden, with or without AADs, after one procedure, or one procedure or more
- 9. Quality of life measurements (SF-36 and AFEQT) at baseline, 3, 6 and 12 months post-index procedure
- 10. Incidence of peri-procedural complications including stroke, PV stenosis, cardiac perforation, esophageal injury, and death
- 11. Acute AF termination rate by ablation
- 12. Rate of conversion to sinus rhythm by ablation
- 13. Ablation procedure duration
- 14. Fluoroscopy time and dose
- 15. Mapping time
- 16. Radiofrequency (RF) time to terminate AF
- 17. Total RF time
- 18. Total delivered energy (mean power x RF duration)
- 19. Total delivered energy (mean power x RF duration) / biatrial surface
- 20. Ablation surface area to terminate AF
- 21. Total ablation surface area
- 22. Blinded baseline Voltage maps before ablation
- 23. TTM compliance (% of transmissions expected vs received at each week post index procedure)

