4.4.1 Exploratory Endpoint Analysis

Endpoints 1-8 will be tested using a Cox proportional hazards model with randomization group and AF strata as fixed effects. Hypotheses will be tested in the following order, and each at a less stringent one-sided alpha level of 0.05, given the exploratory nature of these analyses)

Endpoint 9 will be tested by comparing the QoL score at each visit between tailored and anatomical ablation using a t-test for difference in means. A Shapiro-Wilks test will be used to assess whether the data meets normality assumptions for parametric. Should the normality assumption be violated, a non-parametric method such as the Wilcoxon test will be used instead. The effect of time will also be assessed using a generalized linear mixed model for repeated measures.

Endpoints 10 - 21 and 23 will be tested by comparing tailored and anatomical ablation groups. using a t-test for differences in means. Should the normality assumption be violated, a non-parametric method such as the Wilcoxon test will be used instead.

Endpoint 22 will not undergo any statistical analysis, but the data collected (blinded baseline voltage maps prior to ablation) will be provided to the sponsor in a dataset / spreadsheet format to enable any post-hoc analysis that may be desired.

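### RF time and ablation area to terminate AF are undefined for patients whose AF did not terminate, so the planned t-test or Wilcoxon comparison is biased toward shorter values in the arm that stops ablating earlier

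*SAP*

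**What the plan says.** SAP 4.4 lists as exploratory endpoint 16 "Radiofrequency (RF) time to terminate AF" and as endpoint 20 "Ablation surface area to terminate AF" (numbers 20 and 24 in the protocol). SAP 4.4.1 says "Endpoints 10 - 21 and 23 will be tested by comparing tailored and anatomical ablation groups", "using a t-test for differences in means", with a non-parametric test such as Wilcoxon if normality fails. It names no analysis set, sidedness or alpha for this group, and no rule for a patient whose AF did not terminate. SAP 6.3 plans supportive missing-data analyses for the primary endpoint only. Protocol 6.5.2 has the same t-test or Wilcoxon rule for continuous variables.

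Protocol 5.3.4 sets different stopping points:

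- **Tailored:** "In the Tailored group, the procedure endpoint is sinus rhythm conversion by ablation at dispersion regions" mapped in AF and any later AT. If AF persists once all dispersion areas are ablated, at least one further mapping and ablation cycle is mandatory and two complete re-mappings are recommended.
- **Anatomical:** "In the Anatomical group, the procedure endpoint is isolation of all four PVs". A patient not converted by then is cardioverted.

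Protocol 7.3 adds: "Subjects randomized into the Tailored arm of the study are expected to receive higher RF times, greater ablation area". Table 7 of the protocol collects "Total RF ablation time and RF time to AF termination". It also collects both areas, but only where the navigation system can supply them.

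**The concern.** A time or area to termination exists only if termination happened. With no rule for the rest, the natural execution of SAP 4.4.1 is to test the patients who have a value. That subset is formed after randomisation, by the result of the procedure, and the two arms form it differently. Anatomical values are generally cut off earlier, while the Tailored arm goes on ablating and so can record later terminations.

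The difference between the arms then mixes how quickly RF terminates AF with how long each arm kept ablating. It can reach significance when each minute of RF works equally well in both arms, and it can hide or reverse a real advantage for Tailored. SAP section 3 allows the specified analyses to be used in manuscripts and regulatory submissions, so such a p-value could be published.

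**Working it through.** **The plan's own figure.** The documents give no figure for endpoints 16 and 20. The number per arm used below comes from SAP 4.2.2, which reproduces: HR = ln 0.77 / ln 0.62 = 0.547; log-rank power with 292 patients is 80.0% (exponential survival, 12 months); 292 / 0.78 = 374.4, against 374 stated. That gives 146 per arm.

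**Direction.** Let T be the RF time at which AF would terminate and c the RF time at which ablation stops. Terminators-only data estimate E[T | T ≤ c]. For any fixed distribution of T this falls as c falls, so with equal efficacy the earlier-stopping arm shows the shorter mean. No numerical assumption is needed.

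**Size with fixed stops.** The documents give neither termination rates nor RF times, so the following are assumptions: a constant termination hazard k, equal in both arms, and stops at 30 min (Anatomical) and 60 min (Tailored).

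E[T | T ≤ c] = 1/k − c/(e^(kc) − 1); proportion terminating = 1 − e^(−kc).

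For k = 0.01:

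- c = 30: 100 − 30/(e^0.3 − 1) = 14.3 min; 26% terminate.
- c = 60: 100 − 60/(e^0.6 − 1) = 27.0 min; 45% terminate.

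For k = 0.005 the means are 14.6 and 28.5 min; for k = 0.02 they are 13.5 and 24.1 min. The mean nearly doubles with no true difference.

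**False-positive rate.** Simulation with k = 0.01 in both arms, 146 per arm, two-sided 0.05 (assumed, as the SAP gives none for these endpoints), terminators only. The first three rows let the stopping time vary between patients (mean ± SD, assumed).

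| Stop, Anatomical vs Tailored (min) | t-test | Wilcoxon |
|---|---|---|
| 30 ± 8 vs 35 ± 10 | about 17% | about 13% |
| 30 ± 8 vs 40 ± 12 | about 45% | about 30% |
| 30 ± 8 vs 45 ± 12 | about 72% | about 53% |
| 30 vs 60, fixed | about 100% | about 96% |

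**Other shapes.** A second set of simulations used the same Weibull time to termination in both arms (shape 1 or 1.5, scale 40 min), with stops set so that 10–50% of Anatomical and 70–90% of Tailored patients terminate. The t-test rejects in 97–100% and the Wilcoxon test in 91–100%. With equal stops (70% terminating in each arm) both reject in 5–6%. A log-rank test on all patients, with non-terminators censored at the end of RF, rejects in 4–6% in every scenario.

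**When the arms truly differ.**

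- Weibull shape 1, Tailored hazard twice as high, stops at 8.9 and 48.2 min (20% vs 91% terminating): terminators-only means are 4.3 vs 15.2 min, so the more effective arm looks slower. The censored log-rank test finds the Tailored advantage with 87% power.
- Hazards 0.01 vs 0.08 per min, stops 30 and 60 min: the Tailored mean is 12.5 − 60/(e^4.8 − 1) = 12.0 min against 14.3 min. The sign of the observed difference reverses, although the bias still works against Tailored.

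**The case against.** The strongest case against is one of weight. These are 2 of 23 exploratory endpoints; no superiority claim, sample size, interim or safety decision rests on them. The bias runs against the sponsor's own strategy, so it cannot manufacture a benefit, and Protocol 7.3 already expects more RF and more area in Tailored. The same list compares termination rate (11), conversion to sinus rhythm (12), total RF time (17) and total area (21), which exist whether or not AF terminates. A reader would see the imbalance beside the two endpoints. The SAP is also silent on who enters the test; it does not prescribe terminators only.

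Most of this stands as a limit on importance. It does not repair the test: the neighbouring endpoints give context but leave the p-values for 16 and 20 uninterpretable, and silence on non-terminators is itself the gap.

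Three stronger readings are tempting and are not supported:

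- *Late termination can be seen only in Tailored.* RF totals vary between patients and may overlap, and a CTI line is recommended in either arm for common flutter (Protocol 5.3.4, AT ablation).
- *The analysis is bound to show that Tailored needs more RF.* That follows at equal or similar hazards. With a much higher Tailored hazard the observed sign can reverse.
- *A false positive is practically certain.* That is the result for a large assumed gap in stopping time. Modest gaps with between-patient spread give 13–17%.

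**Conclusion.** The concern holds as a fault in how SAP 4.4.1 handles endpoints 16 and 20. A comparison restricted to patients with a value conditions on a post-randomisation outcome that the stopping rules make unequal, and the Wilcoxon fallback shares the fault. The direction of the bias, toward a shorter time or smaller area in the earlier-stopping arm, follows from the design. That this arm is Anatomical rests on Protocol 5.3.4 and 7.3.

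The size is not fixed by the documents. Under an equal hazard of 0.01 per min and 146 per arm, the false-positive rate lies between about 17% and 100% for the t-test and between about 13% and 96% for Wilcoxon, depending on the assumed gap in stopping time. Conclusions on the primary and secondary endpoints are untouched. The change is worth making because it is cheap and avoids a misleading p-value.

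**What to change.** In SAP 4.4.1:

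1. Take endpoints 16 and 20 out of the t-test/Wilcoxon group.
2. Report terminators-only values descriptively, with the number terminating over the number at risk (n/N) in each arm and no p-value.
3. Analyse AF termination over cumulative RF time in all patients in AF at the first RF application, with non-terminators censored at their own total RF time. Show curves by arm with a log-rank test. Give a hazard ratio only after a proportionality check, since Tailored ablates dispersion areas before completing vein isolation and the hazard per minute may change during the procedure.
4. Do the same for cumulative area, only in patients whose navigation system records it, and state the number missing in each arm.

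SAP section 3 lets the SAP prevail over the protocol, so the edit can be made there alone. Total RF time, RF time to termination and, where available, both areas are already collected (Protocol Table 7). The cost is slightly more analysis work, and the area analysis will rest on incomplete data. If that is thought too much for exploratory endpoints, steps 1 and 2 alone remove the misleading p-value but give no valid comparison between the arms.

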4.5 SAFETY ENDPOINTS

The safety endpoint is a composite endpoint at 12 months of the following: death, cerebrovascular events, or serious treatment-related adverse event. Because the rates of this endpoint which are observed under each of the study arms may or may not prove to be relatively rare (< 5% within a given arm), two methods of analysis are provided, the one which will ultimately be used to analyze the safety endpoint will depend on its rate of occurrence, as observed across the two study groups. The safety endpoint analysis, regardless of the method employed, will be conducted in the Safety population. The same analysis will also be conducted in the mITT and PP populations, since if rare occurrence of the safety endpoint is observed and the few occurrences observed happen to all occur within the mITT/PP populations, then the smaller subject sample sizes will serve to increase the rates/proportions observed in each study arm.

METHOD 1 (safety endpoint occurrence > 5% in each study arm):

The safety analysis will be to compare the AE composite rate per month (defined as the 4th secondary endpoint in Section 1 Protocol Summary) under the Tailored (treatment) arm against the Anatomical (control) arm AE composite rate per month from the time of index procedure until the 12-month follow-up. A two-sided 95% CI will be generated for the rate ratio (λ_t/λ_c) comparing the AE composite rate for the two study arms.

Let λ_c and λ_t denote the rate of composite adverse events for the Anatomical and the Tailored treatment arms, respectively. Given a non-inferiority margin δ , the null and alternative hypotheses are:

$$H_0: \frac{\lambda_t}{\lambda_c} \ge 1 + \delta$$

$$H_1: \frac{\lambda_t}{\lambda_c} < 1 + \delta$$

 λ_t,λ_c , and $\frac{\lambda_t}{\lambda_c}$ will be estimated with a linear fixed effects model with a log link function and a Poisson distribution for the number of adverse events (referring only to those defined under the composite AE endpoint). The outcome of the model is the number of composite AEs for each subject enrolled and randomized to one of the study arms. The model will

include an indicator variable for Study Arm, an offset for the log of the number of weeks each subject remained enrolled in the study will be added (the date of each subject's index procedure will be regarded as their first day on the study). In the event the model fails to converge, it will be refit with a Negative Binomial distribution.

 H_0 is rejected if the upper limit of the 95% confidence interval for $\frac{\lambda_t}{\lambda_c}$ is less than $1+\delta$. If H_0 is rejected, non-inferiority is demonstrated. Based upon the number of months and the expected rate of adverse events, the current study design is under-powered to detect a clinically meaningful (less than 5%) non-inferiority margin for the Tailored treatment arm. Because the null hypothesis test must be conducted under a specified non-inferiority margin, the analysis will use $\delta=0.05$.

METHOD 2 (safety endpoint occurrence (≤ 5% in each study arm):

If both model approaches fail to converge, most likely due to the incidence of the composite AE rates being relatively rare (less than or equal to 5%) under both study arms, then the composite AE endpoint will be treated as a frequency instead of a rate, such that P_1 will be used to denote the proportion defined by the number of composite AEs out of total subjects in the Tailored (treatment) arm and P_2 will be used to denote the proportion defined by the number of composite AEs out of total subjects in the Anatomical (control) arm. The difference in proportions ($P_1 - P_2$) will be reported along with a two-sided exact 95% CI using an exact test statistic with continuity correction if not already defaulted (a Fisher's Exact test may be used if CI can be generated from its statistic for the difference of proportions estimate). Given a non-inferiority margin δ , the null and alternative hypotheses are as follow:

$$H_0: p_1 - p_2 \ge \delta$$

 $H_1: p_1 - p_2 < \delta$

If the upper bound of the 90% CI for (P_1-P_2) is less than $\delta=0.025$, the null hypothesis is rejected, and non-inferiority is demonstrated (2.5% has been allocated as a clinically meaningful non-inferiority margin in the absence of literature). In the event that the composite AEs have a zero occurrence in both study arms, a confidence interval for the difference of proportions cannot be computed, in which case 95% exact CIs for P_1 and P_2 will be reported, and non-inferiority will be considered demonstrated.

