## **VI – STATISTICAL CONSIDERATIONS**

### **6.1 – Design, statistical methodology and analytical procedures**

Standard summary statistics will be calculated for all study variables (demographics and outcomes) by study group and for all patients. For continuous variables, statistics will include means, standard deviation and 95% confidence intervals for means when assumptions of normal distribution are not violated. Median and quartiles may also be presented. Categorical variables will be summarized using frequency distributions.

The analysis for the primary endpoint will be a modified Intention-To-Treat (mITT) analysis, allowing exclusion of some randomized subjects in a justified way:

- Patients that are deemed ineligible after randomization or that do not have any AF ablation will be excluded
- Patients in the Tailored group for whom AF cannot be induced and who undergo conventional ablation will be included in this analysis
- Patients lost to follow-up (death, disability, relocation, or drop-out) during the 3-month blanking period will be excluded
- Patients who complete at least their 3-month follow-up but who are lost to follow-up (death, disability, relocation, or drop-out) before the 12-month follow-up will be included in the analysis and the data will be censored
- Patients who undergo a 3rd ablation procedure (re-repeat procedure) will be included in the analysis but the data will be censored at the time of the 3rd procedure.

A per-protocol (PP) population will also be evaluated and will serve as supportive analyses to the mITT analysis. In the PP analysis, the population will be analyzed according to the treatment actually received at the start of the study, and will consist of patients that met all the inclusion criteria, none of the exclusion criteria, were successfully treated, had no important protocol deviations and attended all the scheduled follow-up visits.

 <small>ARTIFICIAL INTELLIGENCE SERVING HEART DISEASE</small>	CLIPL-01-002-E	CONFIDENTIAL
	CLINICAL INVESTIGATION PLAN	F 09 XX 01 Rev.A Page 33/47

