## **10.2 – Procedures for recording, reporting and analyzing deviations from the Clinical Investigation Plan**

Protocol deviations shall be reported to the Sponsor regardless of whether medically justifiable or taken to protect the patient in an emergency.

Subject-specific deviations will be reported on the Labcorp Risk and Issues Management System (RIMS).

Non-subject specific deviations (e.g. unauthorized use of a study device by a physician who has not signed an investigator agreement, etc.) will also need to be reported to the Sponsor.

Investigators will also adhere to procedures for reporting study deviations to their Ethics Committee or IRB in accordance with their specific reporting policies and procedures.

For reporting purposes, the Sponsor classifies study deviations as important or non-important. Important deviations are defined as changes in the conduct of the trial from that specified in the protocol that compromise the subject's rights, safety, or well-being, or the completeness, accuracy, reliability or scientific integrity of the study data. The following deviations are considered to be important:

1. Enrollment of a patient without written consent
2. Failure to report SAEs
3. Crossovers between the groups
4. Use of other energy than RF for ablation (cryo/chemical)
5. Ablation other than antral PVI in the Anatomical arm for index procedures (e.g. lines other than ICT, EGM ablation, PV encirclement other than antral),
6. Ablation other than PVI ± lines (as defined in 5.3.7 – Redo procedure) in the Anatomical arm for redo procedures,
7. Failure to terminate AF with incomplete mapping in the Tailored group (mono atrial mapping, too short mapping < 20 minutes),
8. Failure to terminate AF with incomplete ablation in the Tailored group, leaving dispersion areas not ablated, without valid justification (for safety reasons at operator's discretion),
9. Failure to terminate AF without a mandatory second mapping/ablation cycle in the Tailored group,

Deviations not classified as important will be considered non-important. Protocol deviations will be classified by the Steering Committee in a blinded fashion. Patients presenting with at least one important deviation will be excluded from the Per-Protocol (PP) analysis.

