4.1.1 The Safety Population

The Safety population will include all randomized Subjects who underwent their first ablation procedure.

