4.1.2 The Modified Intent-to-Treat Population (mITT)

The modified Intention-To-Treat (mITT) set will include all randomized subjects except for:

- Subjects who are deemed ineligible after randomization or who do not have any AF ablation, and
- Subjects lost to follow-up during the 3-month blanking period.

Subjects in the Tailored group for whom AF cannot be induced and who undergo conventional ablation will be included in the mITT analysis.

Subjects who complete at least their 3-month follow-up visit but who are lost to follow-up before the 12-month follow-up visit will be included in the mITT analysis.

Subjects who undergo a 3rd ablation procedure will be included in the analyses but the data will be censored at the time of the 3rd procedure for multiple procedure endpoints.

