4.1.3 The Per-Protocol Population (PP)

The Per-Protocol (PP) analysis set will include only those subjects of either given treatment arm defined as the treatment actually received at the start of the study, and will consist of subjects who met all the inclusion criteria, none of the exclusion criteria, were successfully treated with an index procedure, had no important protocol deviations, and attended the scheduled follow-up visits (did not miss more than one mandatory Holter recording, and TTM compliance >50%).

The PP analysis set will also be used to evaluate endpoints already evaluated using the mITT as the primary analysis set, thus serving as supportive analyses to that of the mITT efficacy analysis.

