4.3 SECONDARY ENDPOINTS

The secondary endpoints are as follow:

- 1. Freedom from AF/AT after one or two procedures at 12 months following index procedure.
- 2. Freedom from AF/AT after a single procedure at 12 months following index procedure.
- 3. The safety endpoint is a composite endpoint, the events of which it is comprised include that of death, cerebrovascular event, or serious treatment-related adverse event at the 12-month timepoint since initial index procedure (this endpoint is inclusive of the Blanking Period marked by the 3 months immediately following the initial index procedure undergone by each enrolled subject).

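### The safety non-inferiority test is repeated in the PP and mITT sets, whose membership depends on what happens after ablation, and the SAP does not say that only the Safety population decides

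*SAP*

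**What the plan says.** The safety endpoint is a 12-month composite of death, cerebrovascular event or serious treatment-related adverse event. SAP 4.3 counts it from the index procedure: "this endpoint is inclusive of the Blanking Period marked by the 3 months immediately following the initial index procedure".

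SAP 4.5 names the main set: "The safety endpoint analysis, regardless of the method employed, will be conducted in the Safety population". SAP 4.1.1 defines it without any exclusion after ablation: "The Safety population will include all randomized Subjects who underwent their first ablation procedure". SAP 4.5 then adds: "The same analysis will also be conducted in the mITT and PP populations". Its reason is that, if the few events all fall inside the smaller sets, the smaller denominators raise the observed rates.

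The other two sets are defined as follows.

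- **PP (SAP 4.1.3).** Members must be successfully treated, have no important deviation and have attended follow-up, which includes that they "did not miss more than one mandatory Holter recording". Protocol 10.2 lists failure to report serious adverse events among the important deviations and states: "Patients presenting with at least one important deviation will be excluded from the Per-Protocol (PP) analysis".
- **mITT (SAP 4.1.2).** All randomized subjects except the ineligible, those not ablated and "Subjects lost to follow-up during the 3-month blanking period". Protocol 6.1 words the last exclusion more widely: "Patients lost to follow-up (death, disability, relocation, or drop-out) during the 3-month blanking period will be excluded".

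Method 2 in SAP 4.5 declares non-inferiority if the upper 90% limit for the difference in proportions is below 2.5 points, or if neither arm has an event. Method 1 uses a rate-ratio limit of 1.05.

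**The concern.** A safety comparison should keep every treated patient who has the event. Here the repeats use sets whose membership depends on surviving and attending, and death is part of the endpoint. The SAP's reason for the repeats covers only the case where all events stay in the smaller set. It does not consider an event that takes the patient out of the set.

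The same decision rule applies in each set, so a repeat could report non-inferiority as demonstrated after its own definition had removed the gravest events. SAP 4.1.3 gives the PP set a supportive role for efficacy. Nothing gives the safety repeats that label or says how a disagreement between sets is resolved. A report could then set a favourable PP or mITT result beside an unfavourable Safety-population result as if they had equal standing.

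**Working it through.** **1. Which events leave which set**

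| Event in an ablated patient | Safety | PP | mITT |
|---|---|---|---|
| Death before the 6-month Holter | kept | removed: the 6- and 12-month Holters, two of three, are missed | see next row if within 3 months; otherwise kept |
| Death within 3 months | kept | removed | removed under Protocol 6.1; unclear under SAP 4.1.2 |
| Disabling stroke within 3 months, patient leaves follow-up | kept | removed if more than one Holter is missed | removed |
| Stroke, patient stays in follow-up | kept | kept if the other conditions are met | kept |
| SAE the site failed to report, found later | kept | removed (important deviation) | kept |

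**2. Inputs**

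The plan gives no event rate, sample size or power for the safety test, so there is no safety figure to reproduce. Arm sizes come from the efficacy calculation in SAP 4.2.2. That calculation reproduces: HR = ln 0.77 / ln 0.62 = 0.547; 146 per arm gives 80.0% log-rank power; 292 / 0.78 = 374.4, against 374 stated. Below, n is 187 per arm (all randomized) or 146 (evaluable). All event counts are assumptions.

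**3. Method 2**

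The upper limit is the value d that solves

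(p1 − p2 − d) / √{[p̃1(1 − p̃1)/n1 + p̃2(1 − p̃2)/n2] × N/(N − 1)} = −1.645,

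where p̃1 and p̃2 are the maximum-likelihood estimates under p1 − p2 = d (Miettinen-Nurminen score limit). The exact unconditional p-value at the 2.5-point margin is given beside it and compared with one-sided 0.05, to match the 90% interval. Counts are Tailored versus Anatomical, and only Tailored events are removed.

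| All treated | Limit (points), p | After removal | Limit (points), p |
|---|---|---|---|
| 2/187 vs 1/187 | 2.71, 0.065: fails | 1/186 vs 1/187 | 1.89, 0.024: passes |
| 3/187 vs 2/187 | 3.01, 0.091: fails | 2/186 vs 2/187 | 2.25, 0.037: passes |
| 4/187 vs 2/187 | 3.74, 0.184: fails | 2/185 vs 2/187 | 2.27, 0.038: passes |
| 2/146 vs 1/146 | 3.45, 0.134: fails | 1/145 vs 1/146 | 2.42, 0.046: passes |
| 4/180 vs 1/180 | 4.37, 0.340: fails | 1/177 vs 1/180 | 1.99, 0.028: passes |
| 3/187 vs 1/187 | 3.48, 0.161: fails | 2/186 vs 1/187 | 2.73, 0.066: still fails |
| 6/187 vs 3/187 | 4.68, 0.334: fails | 3/184 vs 3/187 | 2.60, 0.055: still fails |

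With 2 versus 0 at 187 per arm the limit is 3.18. If both Tailored events are removed, the set holds no events and passes by the zero-event rule.

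**4. Error rate under Method 2**

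Take a true difference of 2.5 points, control rate 1–5%, 187 per arm, and apply the score test by exact binomial enumeration. With no removal, non-inferiority is wrongly shown 3.9–4.9% of the time, in line with the nominal 5%. If the set removes 25% of endpoint patients in both arms, the difference left in the set is 0.75 × 2.5 = 1.875 points and the error is 8.1–8.8%. With 10% removed it is 5.4–6.0%, and with 50% removed 14.9–21.2%. The shares are assumed, and the small loss of denominator is ignored.

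**5. Method 1**

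With equal follow-up, the Poisson 95% upper limit is RR × exp[1.96 √(1/x1 + 1/x2)].

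- 4/180 vs 1/180: 4.00 × exp(1.96 × 1.118) = 35.8.
- 1/177 vs 1/180: 1.017 × exp(1.96 × 1.414) = 16.3.
- 2/187 vs 1/187: 2.00 × exp(1.96 × 1.225) = 22.1.
- 1/186 vs 1/187: 1.005 × exp(1.96 × 1.414) = 16.1.

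All are far above 1.05, so nothing flips.

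**The case against.** The strongest reply is that the safety conclusion already has a set. SAP 4.5 and item 3 of SAP 4.3.1 place the analysis in the Safety population, which keeps every ablated patient. All adverse events are tabulated by arm (SAP 4.5.1), and peri-procedural death and stroke form a separate exploratory endpoint. This stands: no event is hidden and the main result is not biased by set membership. What remains is that the repeats carry a decision rule without a stated rank.

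A reader might infer that no early death can appear in the mITT run. The documents do not establish this. The wording that includes death and disability is in Protocol 6.1 and 6.7. SAP 4.1.2 and 6.3 omit it, SAP 6.3 describes loss as a subject who cannot be located, Protocol 5.2.3 lists death and loss to follow-up as separate reasons for ending participation, and SAP section 3 lets the SAP prevail. On the SAP's wording alone an early death could stay in mITT by default. The PP removal does not depend on this.

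The unreported-SAE route applies to PP only, and matters only if the event is found later; an event never found is missing from every set.

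On size, the flips need Method 2. Its heading assigns it to rates of 5% or less, but its text brings it in when both Method 1 models fail to converge. A Poisson model with events in both arms, as in section 5 of the working, does converge, so under that trigger the low counts would stay with Method 1 and fail either way. The examples also remove events from the Tailored arm only, a pattern for which the documents give no figure.

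Finally, PP is the only set defined by treatment actually received. That is a fair reason to keep a descriptive PP table, but not a second non-inferiority test.

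**Conclusion.** The point holds for the repeat analyses. On the SAP's own text, the PP run drops a patient who dies before the 6-month Holter, although that death is an endpoint event. The mITT run does likewise for early deaths and disability if the protocol's definition of loss to follow-up applies. Removal is partial: strokes in patients who stay in follow-up remain in mITT.

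Under Method 2, removing one to three Tailored events is enough to reverse the decision when counts are low. Larger imbalances, such as 6 versus 3 with three removed, still fail. If a quarter of endpoint patients were removed from both arms, the false non-inferiority rate would roughly double, from 3.9–4.9% to 8.1–8.8%. These sizes rest on assumed counts, assumed removal shares and the reading that Method 2 applies at rates of 5% or less. Under Method 1 the examples checked do not change.

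A reader might conclude that the trial's safety result is compromised. The documents do not support that, because the Safety-population analysis keeps these patients. The risk is a misleading supporting statement, not a wrong main analysis.

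**What to change.** 1. State in SAP 4.5 that the safety non-inferiority conclusion is drawn only in the Safety population.
2. Delete the mITT and PP repeats of the test, or keep them as descriptive tables with no non-inferiority statement. In either case, list by arm the composite events in treated patients whom each set excludes, with the reason for exclusion.
3. Reconcile SAP 4.1.2 with Protocol 6.1 on whether death and disability in the first 3 months count as loss to follow-up.

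Do not build a set that adds back only the excluded patients who had events. That selects on the outcome and inflates the rates.

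The cost is SAP wording, at most two tests fewer and one short listing. No data, visits or patients are added.
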